#### 3.6.2 Exclusion Criteria

- Subject has significant renovascular abnormalities such as renal artery stenosis  $> 30\%$

- Subject has undergone prior renal angioplasty, renal denervation, indwelling renal stents, and/or abdominal aortic stent grafts
- Subject has hemodynamically significant valvular heart disease as determined by Study investigator
- Subject has a life expectancy less than 12 months, as determined by the Study Investigator
- Subject is participating in another clinical study which has the potential to impact their hypertension management (pharmaceutical / device / homeopathic)
- Subject is pregnant, nursing, or of childbearing potential and is not using adequate contraceptive methods
- Subject has active systemic infection
- Subject has renal arteries with diameter(s) < 4 mm in diameter
- Subject has an estimated GFR <15 mL/min per 1.73 m^2 using the Modification of Diet in Renal Disease (MDRD) formula
- Subject had a renal transplant or is awaiting a renal transplant
- Subject has blood clotting abnormalities

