#### 5.7.3 Serious Adverse Event (SAE)

An adverse event that led to:

- Death
- A serious deterioration in the health of the subject, that either resulted in:
  - A life-threatening illness or injury OR
  - A permanent impairment to a body structure or a body function OR
  - An in-patient or prolonged hospitalization OR
  - A medical or surgical intervention to prevent life-threatening illness or injury or permanent impairment to a body structure or a body OR
  - A malignant tumor
- Fetal distress, fetal death or a congenital abnormality or birth defect

Note: A planned hospitalization for a pre-existing condition, or a procedure required by the CIP, without serious deterioration in health, is not considered a serious adverse event.

---

SJM CONFIDENTIAL AND PROPRIETARY

© 2012 – St. Jude Medical Cardiovascular Division: All rights reserved. No portion of this work may be reproduced in whole or in part without the express written permission of St. Jude Medical Cardiovascular Division.

Clinical Investigational Plan: EnligHTN II

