**7.4.2.2 Safety Midterm (6 months) and Long term (2 and 5 years) data**

- The new renal artery stenosis (>50%) and/or aneurysm at the site of ablation per Renal Artery Imaging (CT/MR) will be summarized at 6 months, 2 and 5 years as percentage of patients who have stenosis and/or aneurysm. Kaplan-meier analysis may be performed on the time to the first new renal artery stenosis and/or aneurysm at the site of ablation, as appropriate.
- Renal function change based on eGFR will be summarized by:
  1. Computing the change of the eGFR at 6 months, 2 years and 5 years compared to baseline for each patient with data available in both time points.
  2. Calculating the mean and standard deviation of the eGFR change at those interval

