**7.4.2.3 BP reduction**

The data of

- Change in Ambulatory Blood Pressure parameters at 6 months,
- Change in Office Diastolic Blood Pressure at 6 months,
- Change in Office and Ambulatory Blood Pressure parameters

at 12, 24, 36, 48, 60 months post denervation will be calculated in the same way as described in the calculation of SBP reduction at 6 month (Section 7.4.1)

- The percentage of subjects achieving office SBP < 140 at 6 months visit will be computed as follows:

$$\frac{\text{Number of subjects achieving office SBP < 140 at 6 months visit}}{\text{Number of subjects with data available in 6 months visit}} * 100$$

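### Sections 7.4.2.2 and 7.4.2.3 set no rule for eGFR and BP readings after transplant, dialysis, renal stenting or repeat denervation, which matters mainly in Group C

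*Combined protocol and SAP*

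**What the plan says.** For eGFR, Section 7.4.2.2 prescribes "Computing the change of the eGFR at 6 months, 2 years and 5 years compared to baseline for each patient". The only condition attached is that values exist: "for each patient with data available in both time points". The summary is "Calculating the mean and standard deviation of the eGFR change at those interval". For BP, Section 7.4.2.3 says that the office and ambulatory changes "at 12, 24, 36, 48, 60 months post denervation will be calculated in the same way" as in Section 7.4.1, which also takes every patient with both readings.

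The procedures at issue appear in Section 3.6.2 as entry exclusions only: "Subject had a renal transplant or is awaiting a renal transplant" and "Subject has undergone prior renal angioplasty, renal denervation, indwelling renal stents, and/or abdominal aortic stent grafts". No section says what to do with readings taken after such a procedure during follow-up. Dialysis is not mentioned at all. Under Section 4.9, follow-up runs for 5 years unless the subject dies, is lost, withdraws or the study ends, and sites are asked to make reasonable efforts to retain subjects.

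Section 4.4.3 sets Group C at eGFR 15 to <45 with at least 50 subjects, and Section 7.4 reports each group as well as the total. Section 7.2 states that no hypothesis test is planned.

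**The concern.** The long-term renal objective asks whether treated kidneys keep their function. A reading after transplant describes a donor kidney, so the subject with the worst renal outcome could contribute one of the largest positive changes. A reading on chronic dialysis reflects the treatment and not native function. A BP reading after a second denervation, a renal angioplasty or stent, or another BP device reflects more than the index procedure.

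These events are foreseeable. Section 6.1 lists renal failure and renal artery stenosis as possible adverse events, and Group C starts close to the range where renal replacement is considered. Section 7.4.2 names mean eGFR change as the renal-function result at 2 and 5 years and plans no count of renal replacement to set beside it. With no hypothesis test, the mean is itself the finding that readers will take away.

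The problem is distinct from attrition, because these subjects have values at the visit. It is also distinct from drug changes, because these procedures are not medications.

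**Working it through.** The plan gives no figure to reproduce: Section 7.2 has no power calculation, effect size or SD. The check has two parts.

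**What the rule does.** Sections 7.4.1, 7.4.2.2 and 7.4.2.3 define inclusion by availability of two values. Sections 3.6.2, 4.9, 7.3 and 7.4.3 add no censoring, exclusion or flag for later transplant, dialysis, stenting or repeat denervation. Inclusion therefore follows from the rule plus silence.

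**How far the Group C mean could move.** All inputs here are assumptions: n = 35 subjects with a 5-year value (35/50 = 70% of the minimum size); a typical change of -8 mL/min/1.73 m²; a transplanted subject measured at 55 after entry at 25 (+30), where native function would have fallen to 10 (-15). With k transplants:

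- Reported mean = [(35 - k) × (-8) + k × 30] / 35
- Native mean = [(35 - k) × (-8) + k × (-15)] / 35
- Share hidden = (difference between the two) / (size of the native mean) = 45k / (280 + 7k)

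| k | Reported | Native | Share hidden |
|---|---|---|---|
| 0 | -280/35 = -8.0 | -280/35 = -8.0 | 0% |
| 1 | -242/35 = -6.9 | -287/35 = -8.2 | 45/287 = 16% |
| 2 | -204/35 = -5.8 | -294/35 = -8.4 | 90/294 = 31% |
| 4 | -128/35 = -3.7 | -308/35 = -8.8 | 180/308 = 58% |

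Dropping the transplanted subjects gives -8.0 in every row, which is also milder than the native mean once k is at least 1. This is why exclusion alone is not enough.

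**Second set of assumptions.** Take n = 50, with 46 subjects changing by -6 and 4 reaching kidney failure from a baseline of 20.

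- All 4 transplanted and reading 50: (-276 + 120)/50 = -3.12
- The 4 set to 15, the entry floor: (-276 - 20)/50 = -5.92
- The 4 dropped: -6.00
- The 4 on dialysis and reading about 8: (-276 - 48)/50 = -6.48

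Transplant readings roughly halve the apparent loss. Dialysis readings do not: they show decline.

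**All 500 subjects.** With 5 transplants reading 45 to 60 instead of 15, the shift is 5 × 30/500 = 0.30 to 5 × 45/500 = 0.45. At an assumed SD of 8 to 20, the 95% half-width is 1.96 × SD/√500 = 0.70 to 1.75, so the shift is smaller than the sampling error.

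**BP.** If 1% to 10% of subjects have a later procedure worth a further 10 to 20 mmHg (assumed), the mean reduction is raised by 0.01 × 10 = 0.1 to 0.10 × 20 = 2.0 mmHg.

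**The case against.** **Inclusion is inferred.** A reader might infer that the plan deliberately uses every reading regardless of later procedures. It does not say so. Section 4.9 also lets the investigator withdraw a subject at any time, so some transplanted subjects may have no 5-year value. This stands, but withdrawal would replace one undefined handling with another.

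**Dialysis.** A reader might infer that dialysis would also pass as preserved function. A creatinine-based eGFR on dialysis would normally be very low, so it does not flatter the device. Those values are uninterpretable, which is a different reason to set them aside.

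**Data capture.** A reader might infer that these procedures go unrecorded, because neither Table 1 nor Appendix H names a later-procedure form. The documents do not support that. Section 5.7.8 requires all serious events on an eCRF whatever their cause, Section 12.3.2 has them adjudicated, and Section 8 has the eCRFs cover device exposure and other therapies. Appendix H lists form titles only, with data points held separately. The one real doubt is an elective repeat denervation: Section 5.7.3 does not count as serious "A planned hospitalization for a pre-existing condition" when there is no serious deterioration in health.

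**Size.** The event counts are assumed. Section 3.6.2 excludes anyone awaiting a transplant, 4 of 35 would be 11%, and Group C may exceed 50. All of this stands, so zero and one event belong in the range.

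**Descriptive aim.** No test is affected, and BP change regardless of later treatment is a legitimate summary. That is a reason to keep the all-readings BP line, not a reason to show it alone.

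**Conclusion.** The point holds as a gap with a predictable direction for transplant and for repeat BP procedures. The available-pair rule has no condition on intervening procedures, and as written it would average a graft eGFR into a renal safety result as a gain. The concern is concentrated in Group C. There, the share of decline hidden runs from nothing with no transplants, through 16% with one, to 31% and 58% with two and four, on the assumed 35 subjects and changes of -8, +30 and -15. For all 500 subjects the effect is likely small. For BP it is 0.1 to 2.0 mmHg under the assumed ranges. A reader might take the upper percentages as the expected distortion, but the documents give no event rate, so they are illustrations. The change should be made, because it is cheap and Group C is where renal harm matters most.

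**What to change.** **Section 7.4.2.2.** Leave eGFR values after transplant or the start of chronic dialysis out of the change as measured. Report the number of subjects with renal replacement beside the mean at each time point, overall and by group. Add a line in which their last value before renal replacement is carried to later visits, since leaving them out alone also understates decline.

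**Section 7.4.2.3.** Keep the all-readings BP change at 12 to 60 months. Beside it, show the change using only readings before any repeat denervation, renal artery angioplasty or stent, or other BP device, with the number of subjects affected.

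**Identifying the subjects.** Use the SAE and ADE reports (Section 5.7.8) and the eCRF data on other therapies (Section 8). Add a yes/no and date item to the follow-up form only if the existing CRFs do not capture these procedures, because an elective repeat denervation may not be reported as an SAE.

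**Cost.** A few extra table lines, at most one form item at visits already held, and possibly less favourable long-term figures.

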##### **4.3.1 Blood and Urine Analysis**

Blood and urine samples will be collected and analyzed as listed below.

- Serum Creatinine
- Estimated GFR (eGFR)

---

SJM CONFIDENTIAL AND PROPRIETARY

© 2012 – St. Jude Medical Cardiovascular Division: All rights reserved. No portion of this work may be reproduced in whole or in part without the express written permission of St. Jude Medical Cardiovascular Division.

Clinical Investigational Plan: EnligHTN II

- Hemoglobin A1c
- Fasting glucose
- Fasting insulin
- Urine albumin-creatinine ratio
- Pregnancy test (only at baseline)

A true numeric value for the estimated GFR must be provided. If your local laboratory does not report the eGFR value beyond 60 mL/min/1.73 m^2 the center should use a sponsor-approved calculation tool to generate the value. The sponsor will provide an approved website(s) for this calculation to study centers.

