## 4.4 Subject Group Assignment

Subjects who have met all of the baseline and enrollment criteria will be assigned to one of the following groups:

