### 4.4.3 Group C: (minimum of 50 subjects)

- Office systolic Blood Pressure  $\geq 140$  mmHg
- Subject is taking  $\geq 3$  anti-hypertensive medications (including 1 diuretic), or subject has documented drug intolerance to 2 or more of the 4 major classes of anti-hypertensives (ACE/ARB, Calcium Channel Blockers, Beta Blockers, or diuretic) and is unable to take 3 anti-hypertensive drugs.
- Patient has an estimated  $\geq 15$  GFR  $< 45$  mL/min per  $1.73 \text{ m}^2$  using the Modification of Diet in Renal Disease (MDRD) formula

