## **7.4 Data Analysis and Reporting**

In general data analysis will be performed across all subjects, as well as within each of three groups (Group A, B and C), based on Primary Analysis population unless otherwise specified.

The data collected will be presented using the appropriate summary statistics. Continuous data will be summarized using descriptive statistics (mean, number of observations, standard deviation, minimum and/or maximum values) and categorical data will be summarized using frequencies and percentages.

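### Group C appears to be selected on the same single eGFR reading that serves as its baseline, so its mean eGFR change is biased upward and may understate early renal loss

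*Combined protocol and SAP*

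**What the plan says.** Four parts of the combined protocol and SAP bear on this.

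- **Grouping.** Section 4.4 says "Subjects who have met all of the baseline and enrollment criteria will be assigned to one of the following groups". Groups A and B require an eGFR of at least 45; Group C takes 15 to below 45. Only eGFR separates Group C from Group B. The section heading for C reads "Group C: (minimum of 50 subjects".
- **Schedule.** Table 1 (section 4) marks one pre-procedure eGFR, at the confirmatory visit, and section 4.3.1 adds that "A true numeric value for the estimated GFR must be provided". When a subject is re-evaluated, section 4.3 repeats office blood pressure, the medication log and ambulatory blood pressure, but does not list eGFR. Follow-up values come at 6, 12, 24 and 60 months (section 4.8.5).
- **Analysis.** Section 7.4.2.2 specifies "Computing the change of the eGFR at 6 months, 2 years and 5 years compared to baseline", using subjects who have both values, and then takes the mean and SD. Section 7.4 applies this to all subjects "as well as within each of three groups (Group A, B and C), based on Primary Analysis population".
- **Design.** The study is single-arm (section 7.1) with no hypothesis test (section 7.2). Section 7 has no second baseline and no adjustment for baseline.

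**The concern.** A measured eGFR is the subject's underlying level plus visit-to-visit noise. Taking subjects because a reading was low picks up, on average, readings whose noise was negative. Subtracting that same reading from a later one gives a positive expected change even when nothing has happened to the kidneys.

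The direction matters because this is a safety objective. In Group C, the subjects with the least renal reserve, the shift works against detecting loss. In a single arm summarised by mean and SD, nothing in the output separates the shift from a treatment effect. Groups A and B are selected on readings of 45 or more and are shifted the other way.

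**Working it through.** The plan states no eGFR mean, SD, reliability or margin, so there is no figure of its own to reproduce. The size has to be bracketed.

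**Inputs from the documents:** Group C window 15 to below 45; minimum n = 50; one pre-procedure reading; raw difference from baseline.

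**Assumed inputs:** within-subject SD *s* of 3, 5 or 8 mL/min/1.73 m2, independent between visits; true eGFR in the source population either broad, N(60, 20), N(70, 20) or N(75, 22), or concentrated low, N(35, 10) as in a renal clinic, or uniform on 15–60. No true change.

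**Formula (normal sources).** With true mean μ and SD σ, let S² = σ² + s². The expected spurious change in Group C is

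(s²/S²) × (μ − m), where m is the mean of a N(μ, S²) reading truncated to 15–45.

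**Example, N(70, 20):**
- s = 3: s²/S² = 9/409 = 0.0220; m = 36.09; shift = 0.0220 × 33.91 = +0.75
- s = 5: 25/425 = 0.0588; m = 35.92; shift = 0.0588 × 34.08 = +2.00
- s = 8: 64/464 = 0.1379; m = 35.53; shift = 0.1379 × 34.47 = +4.75

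**All sources** (Group C by formula, or by simulation for the uniform source; A/B by simulation), for s = 3 / 5 / 8:

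| Source | Group C | Groups A/B |
|---|---|---|
| N(60, 20) | +0.6 / +1.5 / +3.5 | −0.2 / −0.5 / −1.2 |
| N(70, 20) | +0.7 / +2.0 / +4.8 | −0.1 / −0.3 / −0.7 |
| N(75, 22) | +0.7 / +1.9 / +4.6 | −0.1 / −0.2 / −0.5 |
| N(35, 10) | +0.2 / +0.5 / +1.2 | −1.3 / −3.2 / −6.8 |
| Uniform 15–60 | +0.2 / +0.4 / +1.1 | −0.6 / −1.7 / −4.1 |

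**Against sampling noise.** The SE of the mean change at n = 50 from measurement error alone is s√2/√50 = 0.2s, that is 0.6, 1.0 and 1.6. At s = 5 or 8 the shift exceeds this in every broad model. In the renal-clinic and uniform models it is below it at every s.

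**Effect on a real loss.** With N(70, 20) and s = 5, a true mean loss of 2 appears as −2 + 2.0 = 0, and a loss of 4 as −4 + 2.0 = −2.0. With N(35, 10) and s = 5, a loss of 2 appears as −2 + 0.5 = −1.5.

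**All subjects pooled.** In the broad models the shift is between 0 and −0.2, because the groups nearly cancel and only the floor at 15 still selects. If the whole sample followed N(35, 10) with s = 8, it would be 0.390 × (35 − 36.60) = −0.6.

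**Change from 6 months.** The 6-month value plays no part in selection. Under the same models, the simulated Group C change from 6 months to a later visit was essentially zero.

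**The case against.** The strongest reply is that the documents never say one reading serves both purposes. Section 4.4 does not name the eGFR that assigns the group, and section 7.4.2.2 says only baseline. Section 4.1 has medical records checked against the criteria before consent and allows baseline information to come from hospital records. If subjects reach Group C because a low eGFR was already known, the confirmatory reading is less strongly selected. With N(70, 20) and s = 5, also requiring an independent record value of 15 to below 45 cuts the shift from +2.0 to +1.1. This stands as a limit on size and certainty. It does not remove the point: the confirmatory reading is the only candidate that the visit schedule describes, and the shift shrinks without vanishing.

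The mean eGFR change is also not the only renal signal. Creatinine and urine albumin-to-creatinine ratio are collected (section 4.8.5). Renal failure and acute renal injury are listed events (section 6.1), serious events are reported whatever their cause (section 5.7.8), and an independent committee adjudicates them (section 12.3.2). The summary is secondary and descriptive. All of that is correct and lowers the stakes, but a descriptive mean can still be biased, and its SD does not show it.

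A reader might go further and infer that the plan hides renal loss in Group C, or makes C look safer than A and B. The documents support neither. Concealment requires a true loss no larger than a shift whose size rests wholly on assumed variability. The shift is also roughly constant, so it would not mask progressive loss at 2 or 5 years. No between-group comparison of eGFR change is specified.

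**Conclusion.** The concern holds as a bias of known direction and unknown size in one subgroup summary. If the confirmatory eGFR is both the grouping value and the baseline, as the schedule strongly implies, Group C's mean change is shifted upward at every follow-up visit. This matters most at 6 months, where early loss may be understated or concealed. For a within-subject SD of 3 to 8, the shift is about +0.6 to +4.8 mL/min/1.73 m2 with a broad source population and +0.2 to +1.2 with a renal-clinic or uniform 15–60 source, and less with prior record screening. Groups A/B shift by −0.1 to −1.2 in the broad models and −0.6 to −6.8 in the others. The all-subjects mean is nearly unaffected in the broad models. These figures depend on the assumed distributions and on independent errors between visits.

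**What to change.** In section 7.4.2.2:

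1. Beside change from baseline, report within each group the change in eGFR from 6 months to 24 and 60 months.
2. Name the reading used for grouping and for baseline, and state that Group C's change from baseline is subject to upward regression to the mean.
3. As a sensitivity analysis only, record the last eGFR in the medical record (value and date, distinct from the confirmatory sample). Repeat the renal table with groups defined by that value, and flag subjects who have none.

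The cost is one extra table from data already scheduled and one CRF field, with the sensitivity repeat of the renal table; no added visit or sample. There are three drawbacks. The table from 6 months cannot show loss before 6 months, so it supplements change from baseline and cannot replace it. In the sensitivity table, about 12–36% of Group C could fall at or above 45 in the broad models (6 to 18 of 50), and about 5–16% in the renal-clinic and uniform models; for this reason the main grouping should stay as it is. The Group C figure may also become less favourable.

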**7.4.2.3 BP reduction**

The data of

- Change in Ambulatory Blood Pressure parameters at 6 months,
- Change in Office Diastolic Blood Pressure at 6 months,
- Change in Office and Ambulatory Blood Pressure parameters

at 12, 24, 36, 48, 60 months post denervation will be calculated in the same way as described in the calculation of SBP reduction at 6 month (Section 7.4.1)

- The percentage of subjects achieving office SBP < 140 at 6 months visit will be computed as follows:

$$\frac{\text{Number of subjects achieving office SBP < 140 at 6 months visit}}{\text{Number of subjects with data available in 6 months visit}} * 100$$

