#### 3.6.1 Inclusion Criteria

- Subject is  $\geq 18$  years of age at time of consent
- Subject must be able and willing to provide written informed consent
- Subject must be able and willing to comply with the required follow-up schedule
- Subject has office Systolic Blood Pressure  $\geq 140$  mmHg at confirmatory visit
- Subject has a daytime mean Systolic Ambulatory Blood Pressure  $> 135$  mmHg within 90 days prior to procedure
- Subject has established hypertension (diagnosed  $\geq 12$  months prior to baseline) and is on a guideline based drug regimen at a stable and a fully tolerated dose consisting of  $\geq 3$  anti-hypertensive medications (including 1 diuretic), or subject has documented drug intolerance to 2 or more of the 4 major classes of anti-hypertensives (ACE/ARB, Calcium Channel Blockers, Beta Blockers, or diuretic) and is unable to take 3 anti-hypertensive drugs.

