### **7.3 Analysis Population**

All patients who have signed a Patient Informed Consent (PIC) will be considered enrolled in the study. However, Primary Analysis population will include those patients that have signed a PIC, and had the EnligHTN™ Renal Denervation System enter his/her body. The sample size of 500 are those subjects in the Primary Analysis population.

---

SJM CONFIDENTIAL AND PROPRIETARY

As Treated population will include all subjects in whom renal denervation was performed in a minimum of one renal artery per kidney (according to the Instructions for Use).

It is anticipated that there may be subjects who have enrolled in the study but are not included in the Primary Analysis population or As Treated population, such as:

- Subjects who are enrolled but do not meet baseline inclusion or exclusion criteria before the procedure; these are considered the screen failure population.
- Procedurally excluded populations will include subjects who have enrolled in the study and start the procedure, but do not have the EnligHTN™ Renal Denervation System enter his/her body, due to their anatomy, circumstances related to the procedure, or physician judgment.

Subjects that withdraw from the investigation will not be replaced in any analysis population.

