### **7.4.1 Primary objective**

The mean reduction of office SBP at six (6) months of the study will be analyzed by:

1. Computing the reduction of SBP measurements at 6 months compared to baseline for each patient with data available in both time points.
2. Calculating the mean and standard deviation of the SBP reduction at 6 months

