### **7.4.2 The Secondary objectives**

#### **7.4.2.1 Safety Acute data (30 days post procedure)**

- The peri-procedural events within 30 days post procedure will be summarized as percentage of patients defined as:

$$\frac{\text{Number of subjects with peri procedural events within 30 days post procedure}}{\text{Number of subjects at baseline for that population}} * 100$$

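### The 6-month control rate (office SBP below 140) is calculated only among subjects with a 6-month value, so it may be overstated if those without one are controlled less often

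*Combined protocol and SAP*

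**What the plan says.** Section 7.4 sets the default analysis set: analyses are run overall and within Groups A, B and C, "based on Primary Analysis population unless otherwise specified". Section 7.3 sizes that set ("The sample size of 500 are those subjects in the Primary Analysis population") and adds that "Subjects that withdraw from the investigation will not be replaced in any analysis population".

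Section 7.4.2.3 departs from the default for the control rate. Its numerator is "Number of subjects achieving office SBP < 140 at 6 months visit" and its denominator is "Number of subjects with data available in 6 months visit". The primary endpoint in section 7.4.1 follows the same available-data approach: the reduction is computed "for each patient with data available in both time points".

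Three other places bear on the point:

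- Section 3.6.1 requires an office systolic pressure of at least 140 mmHg at the confirmatory visit (the criterion beginning "Subject has office Systolic Blood Pressure"), so no eligible subject is controlled at entry.
- Section 4.9 lists death, loss to follow-up and withdrawal as ways follow-up can end. It asks that a withdrawing subject attend a final visit that includes office blood pressure.
- Section 4.8 gives the 6-month visit a window of ±30 days.

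Section 7 contains no imputation rule, no analysis counting missing values as not achieved, no sensitivity analysis for missing data and no expected dropout rate. It does not say whether a pressure taken at a withdrawal visit can serve as the 6-month value.

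**The concern.** The objective in section 3.2 is a percentage of subjects. The formula delivers a percentage of those who were measured at 6 months. The two agree only if subjects without a value are controlled as often as those with one.

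There are reasons to expect otherwise. Every eligible subject starts at or above 140 mmHg, so one with no later value was last confirmed as uncontrolled. A subject who dies before 6 months cannot have achieved control at 6 months, yet leaves the denominator. Section 4.9 also lists non-compliance among the reasons for ending participation, and poor control is plausible in such subjects, although the documents give no data on it.

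What is at stake is the reading of a headline-type percentage. A control rate is easily quoted as applying to everyone treated. In a single-arm study there is no comparator in which the same loss would partly cancel.

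**Working it through.** There is no stated figure to reproduce. The documents give no expected control rate or dropout rate, and section 7.2 says that no power analysis or hypothesis test will be performed. The check is therefore algebra plus a range of assumed inputs.

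**Inputs from the plan**

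- Population: N = 500 (section 7.3).
- Smallest planned group: 50 subjects (sections 4.4.2 and 4.4.3).
- Denominator rule: section 7.4.2.3.

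**Assumed inputs, not in the documents**

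- p, the control rate among those with a 6-month value: 30% to 50%.
- m, the share without a value: 5% to 20%.
- q, the control rate among those without a value: from 0 to 100%.

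**Formulas**

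- Planned rate = p.
- Full-population rate = p(1 − m) + qm.
- Overstatement = p − [p(1 − m) + qm] = m(p − q). This is positive only when q < p.
- With missing counted as not achieved (q = 0), the rate is p(1 − m). The planned figure then exceeds it by a factor of 1/(1 − m): 1.05 at m = 5%, 1.11 at 10% and 1.25 at 20%.

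**Results for p = 40%, N = 500**

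| Missing | Achieved / measured (planned) | q = 0 | q = p/2 | q = p | q = 100% |
|---|---|---|---|---|---|
| 5% | 190/475 = 40.0% | 38.0% | 39.0% | 40.0% | 43.0% |
| 10% | 180/450 = 40.0% | 36.0% | 38.0% | 40.0% | 46.0% |
| 15% | 170/425 = 40.0% | 34.0% | 37.0% | 40.0% | 49.0% |
| 20% | 160/400 = 40.0% | 32.0% | 36.0% | 40.0% | 52.0% |

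Worked line at 10% missing: with q = 0, 180/500 = 36.0%. With q = 20%, (180 + 0.20 × 50)/500 = 190/500 = 38.0%. With q = 40%, (180 + 20)/500 = 40.0%.

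Across the assumed range with q = 0, the gap is m × p. It runs from 0.05 × 30 = 1.5 points to 0.20 × 50 = 10.0 points.

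For scale, the 95% half-width at p = 40% and N = 500 is 1.96 × √(0.4 × 0.6/500) = 4.3 points. At 10% missing, the gap is 4 points if no missing subject is controlled and 2 points if they are controlled half as often.

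In a group at its minimum of 50 with 20% missing, the planned figure is 16/40 = 40%, against 16/50 = 32% with missing counted as not achieved.

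**The case against.** The formula is openly stated and matches the plan's other measured endpoints: the mean reduction in section 7.4.1 and the eGFR change in section 7.4.2.2 also use available data. The endpoint is one of several secondary ones in a descriptive study, so no error rate depends on it. Counting every missing value as not achieved is itself a strong assumption: Groups B and C admit subjects from 140 mmHg, and a treated subject near that level who misses a visit could well be below it. A general missing-data rule that imputed 6-month pressure would also yield a control status for everyone. All of this is fair. It argues for showing both percentages rather than replacing one with the other. It does not remove the need to edit the stated denominator.

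Three stronger readings are tempting, and the documents do not support them.

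- A reader might infer that every death, withdrawal and missed visit is dropped. Only those leaving no 6-month value are. Later deaths and withdrawals are unaffected, and the final-visit pressure in section 4.9 might fall inside the ±30-day window.
- A reader might infer that the plan contradicts itself, because section 7.4.2.1 divides 30-day events by "Number of subjects at baseline for that population". That section counts whether an event occurred; section 7.4.2.3 classifies a measurement taken at a visit. Different denominators are natural, and a subject lost before day 30 with no reported event would count there as event-free. It is no precedent for treating missing as failure.
- A reader might take the 8-point gap in the table as the expected bias. It needs 20% missing and no missing subject controlled, both assumed. At 15% missing the bounds are 34% to 49%, which lie on both sides of 40%.

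**Conclusion.** The point holds in a limited form. As written, section 7.4.2.3 reports control among those measured at 6 months, and nothing elsewhere in the plan supplies the rate among all treated subjects. The figure may be overstated, by m(p − q), if subjects without a value are controlled less often than those with one. Entry at or above 140 mmHg and the handling of deaths make that direction probable, but no data in the documents establish it.

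On the assumed case of p = 40% and m = 10%, the overstatement is 4 points, 2 points or nil, according to whether missing subjects are controlled never, half as often or equally often. The true size depends on a missing rate that the plan does not give. This is a worthwhile improvement to a descriptive secondary result and does not threaten the study's validity.

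**What to change.** In section 7.4.2.3, keep the available-data percentage and add beside it, overall and for Groups A, B and C, the percentage over all Primary Analysis subjects, with deaths before 6 months and other missing values counted as not achieved. Report the number without a 6-month value by reason, overall and by group. State whether an office pressure from the withdrawal visit in section 4.9 counts when it falls within the 6-month ±30-day window.

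The cost is wording and one extra table line; no new visits, data or subjects are needed. The downside is that a less favourable figure appears, and that it is conservative if some missing subjects were in fact controlled. Printing both percentages with the missing counts lets the reader judge.
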